9.6 DATA MANAGEMENT

Data management information is as follows:

- The primary data collection of the Crovalimab Silo is coordinated by IPIG and the clinical research organization ICON.
- The data transfer process is described in the Crovalimab Silo data transfer agreement.
- The MAH will approve the eCRF specifications for this study. Source data will be entered into the EDC system built by ICON and the IPIG Registry.
- ICON and the IPIG Registry will produce a Data Quality Plan that is approved by the MAH, which describes the quality checking to be performed on the collected data points by ICON.
- The eCRFs and correction documentation will be maintained in the EDC system audit trail. System backups for data stored at ICON and the IPIG Registry and records retention for the study data will be consistent with ICON and the IPIG Registry standard procedures.
- Pseudonymized data will be transferred electronically as described in the Crovalimab Silo data transfer agreement from ICON/IPIG Registry to the MAH. The MAH standard procedures will be used to handle and process the electronic transfer of these data.
- ICON/IPIG Registry will comply with the MAH procedures regarding content, archiving and records management of process documents defined in MAH reference model (RRM).

Following the extraction from the data source, pseudonymized data will be stored at ICON/IPIG Registry. Access to the data will be restricted to MAH. Only pseudonymized individual patient data will be provided to Roche/Genentech.

9.7 DATA ANALYSIS

Patient demographic and clinical characteristics will be described separately for all participants with PNH, participants who experience an AESI, and participants with PNH who are pregnant and their infants.

The number of participants with PNH included in the study and the number of participants with PNH who complete the study and discontinue early will be summarized. The reasons for study discontinuation will also be summarized. Characteristics of these discontinued study participants will be compared with those who complete the registry.

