6. MILESTONES

Milestone ^a	Planned Date
Registration of protocol in the E.U. PAS register	Q3 2025
First data extraction	Q1 2026
Annual interim report #1	Q4 2026
Annual interim report #2 ^b	Q4 2027
Annual interim report #3	Q4 2028
Annual interim report #4 ^b	Q4 2029
Annual interim report #5	Q4 2030
Annual interim report #6 ^b	Q4 2031
Last data extraction	Q2 2032
Final report of study results (CSR)	Q4 2032
Registration of the results in the E.U. PAS register	To be determined

CSR=Clinical Study Report; FDA=Food and Drug Administration; PAS=post-authorization study; PSUR=Periodic Safety Update Report; Q=quarter.

^a Study progress will be provided in every PSUR.

^b Additional interim report for U.S. FDA submission only.

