Prospective data collection will commence at the initiation of treatment for participants who began therapy with crovalimab on or after the start of the Crovalimab Silo registry (illustrated as Patient A in [Figure 2](#)). For participants who began treatment with crovalimab before the Crovalimab Silo was established, retrospective data will be collected from the Core Registry into the silo, if available; while prospective data

collection will begin from the time of silo enrollment (illustrated as Patient B in Figure 2). The MAH anticipates very few cases in this last scenario.

Figure 2 Study Design for PNH in the Crovalimab Silo

IPIG = International PNH Interest Group; PNH = paroxysmal nocturnal hemoglobinuria.

The planned start date for the Crovalimab Silo refers to the date when information about the first participant in the Crovalimab Silo will be recorded in the database, which is projected to be in Q1 2026. The last data extraction and planned end of the registry, based on a planned data collection in the Crovalimab Silo, is projected in Q2 2032.

Participants' visit schedules will follow SOC. Participants' data are expected to be entered in the electronic data capture (EDC) system by the clinicians and/or their qualified designee at the time of registry enrollment and approximately every 6 months thereafter. In addition, participants and/or their parents/legally authorized representatives have the option to complete electronic patient-reported outcome (ePRO) questionnaires (i.e., the FACIT-Fatigue questionnaire) at registry enrollment, and every 6 months thereafter.

If a participant withdraws from the IPIG registry, the date and reason will be recorded in the electronic Case Report Form (eCRF), with efforts made to obtain this information. Registry site termination may happen due to inadequate participant recruitment or non-compliance with protocols, guidelines, or regulatory requirements. If a clinician withdraws, the MAH should be notified in advance, and a new clinician will be trained and identified to take over patient referrals.

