9.2.2 Inclusion/Exclusion Criteria

To evaluate AESIs and other SAEs and AEs for all participants with PNH:

Participants with PNH included in the SDU study will meet the same inclusion and exclusion criteria from the Crovalimab Silo listed below:

- Inclusion criteria:
 - Participants with PNH confirmed by flow cytometry.
 - Participant and/or parent/legally authorized representative provide written informed consent/assent to participate in the Core Registry and the Crovalimab Silo prior to any registry-related data collection, in a manner approved by the Institutional Review Board (IRB)/Independent Ethics Committee (IEC) and local regulations.
 - Participants with PNH currently being treated with or who start crovalimab during the study period.
- Exclusion criteria:
 - Participants with PNH participating in an interventional PNH clinical trial while receiving crovalimab (i.e., in combination with other therapy), with exception of

participants with PNH participating in the extension period of COMMODORE/COMPOSER Roche studies and Post Trial Access Programs.

The exclusion criteria for all participants will also be applicable to assess crovalimab exposure during pregnancy, as well as pregnancy, infant, and breastfeeding outcomes.

To evaluate AEs and SAEs during pregnancy and pregnancy outcomes:

The following additional inclusion criteria will be applicable:

- Crovalimab exposure during pregnancy or 9 months before DOC

To evaluate infant AEs and SAEs and infant and breastfeeding outcomes:

The following additional inclusion criteria will be applicable:

- Breastfeeding infant
- Infant younger than 12 months of age

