9.2.3 Participant Follow-up

The follow-up period will be the time period from index date (as defined in Section 9.2.1) until the end of the study or censoring, whichever comes first.

To evaluate AESIs and other AEs and SAEs for all participants with PNH, the date of censoring will be defined as the earliest occurrence of any of the following events:

- Consent withdrawal
- Site termination
- Crovalimab treatment discontinuation¹ (with an extra follow-up period after discontinuation)
- Enrollment into an interventional clinical trial²
- Death

To assess safety events during pregnancy and breastfeeding, including pregnancy and infant outcomes, additional censoring events will be defined:

- Date of delivery (for pregnancy safety and outcomes)
- First year of the infant's life (for safety and infant outcomes)
- On the date when breastfeeding stops or first year of the infant's life (for breastfeeding)

[figure not shown]
¹ For participants with PNH censored due to crovalimab treatment discontinuation, follow-up will continue up to 12 months if the participant does not start a new complement inhibitor or for 12 weeks if the participant starts a new complement inhibitor.

² To preserve the integrity of data collected for any interventional therapy for PNH in clinical studies, as well as to avoid duplicate safety reporting, participant data collection will be paused from the Crovalimab Silo and the Core Registry when participants enroll in an interventional clinical study for a PNH therapy.

Note: Safety events from the mother will continue to be recorded even after pregnancy ends, delivery, or the cessation of breastfeeding. Similarly, infant safety events will also continue to be recorded through their first year of age if breastfeeding is suspended.

Evaluation of pregnancy and infant outcomes during crovalimab exposure will rely on prospectively collected data within the Crovalimab Silo only for participants who enroll into the silo before being pregnant. However, for participants who enroll into the Crovalimab Silo while being pregnant, retrospective data on crovalimab exposure and outcomes will be incorporated into the silo, if such data are available from the Core Registry. Data for participants whose pregnancy outcomes occur before their enrollment in the Crovalimab Silo will not be obtainable. Very few instances are expected in these latter two scenarios due to the timing of drug approvals and site initiations in the Core Registry (see Figure 3).

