9.9.4 Loss to Follow-up

Given the maximum follow-up duration of 7 years, the study may experience a significant proportion of discontinued participants. To detect potential biases, the characteristics of these discontinued participants will be compared with those who complete the registry. Specific Concerns for PNH and Pregnancy In parallel, the MAH will explore options to renegotiate with the IPIG registry if needed to extend the study duration, ensuring a minimum five-year follow-up is met for all enrolled participants with PNH and pregnant participants with PNH are included. Likewise, the MAH will investigate alternative approaches for data collection to supplement enrollment if necessary.

Potential confounding factors affecting pregnancy outcomes will be assessed and contextualized, particularly those related to PNH treatment. It is unlikely that participants with PNH who are pregnant will stop crovalimab therapy entirely due to the severity of PNH relapses.

Moreover, existing evidence suggests PNH is associated with certain pregnancy complications and adverse outcomes, indicating that PNH itself may act as a confounder in the relationship between crovalimab and pregnancy-related outcomes evaluated in this study. Residual confounding from unmeasured factors is anticipated, and its impact on study outcomes cannot be predicted.

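### The attrition check compares discontinued participants with registry completers, but with rolling entry and one closing date completer status depends partly on when a participant entered

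*Protocol*

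**What the plan says.** Section 9.7 states: "Characteristics of these discontinued study participants will be compared with those who complete the registry". The sentences before it add counts of those who complete and those who leave early, and a summary of the reasons. Section 9.9.4 gives the purpose: "To detect potential biases, the characteristics of these discontinued participants will be compared with those who complete the registry". The same section warns that "the study may experience a significant proportion of discontinued participants". No other check for attrition bias is described.

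The features that matter for this comparison are:

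- **Entry is rolling.** Section 9.2.2 admits "Participants with PNH currently being treated with or who start crovalimab during the study period".
- **Follow-up ends on a common date unless censored earlier.** Section 9.2.3 runs it "until the end of the study or censoring, whichever comes first".
- **The calendar.** Section 9.1 gives a silo start "which is projected to be in Q1 2026" and puts the last data extraction and the planned end of the registry in Q2 2032.
- **Stopping crovalimab is not the same as leaving.** Section 9.2.3 continues follow-up for 12 months after stopping, or for 12 weeks if a new complement inhibitor is started.

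The protocol does not define completing the registry. It plans no allowance in this comparison for entry date or length of follow-up.

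**The concern.** With staggered entry and one closing date, being a completer mixes two things: not having left, and not having had long in which to leave. Someone who enters in the first months must stay about six years to count as a completer; someone who enters in the last year must stay only months. The discontinued group is therefore weighted towards early entrants and the completers towards late ones, even when everyone leaves at the same rate.

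This does no harm if early and late entrants are alike. If they differ, for example in country or prior C5 inhibitor use, the table will show a difference that reflects entry date and not selective drop-out. A drift in the other direction can cancel a real association. Section 9.5 ties enrolment to approval timing and uptake in each country, and section 9.2.2 admits trial-extension and post-trial-access participants who are already on crovalimab. Some drift is therefore plausible, although the protocol does not state any.

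What is at stake is the interpretation of the attrition check. A reader could take an entry-date artefact for informative drop-out, or be wrongly reassured.

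**Working it through.** The protocol gives no figure for this comparison, so there is none to reproduce.

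**Inputs from the protocol.** Q1 2026 to Q2 2032 spans 6.0 to 6.5 years; I use the midpoint, T = 6.25. (Section 9.5 speaks of a 7-year registry, which these dates do not reach. The mechanism is the same for either length.) The expected enrolment is 300.

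**Assumptions, none of them in the protocol.** A constant discontinuation hazard h of 0.05, 0.10 or 0.15 per year; uniform entry over A years; a binary characteristic whose share falls linearly from 80% to 40% over accrual (average 60%) and has no effect on discontinuation.

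**Step 1: chance of being classed as discontinued, by entry time e.** This is 1 - exp(-h(T - e)). At h = 0.10:

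- entry at year 0: 1 - exp(-0.625) = 46.5%
- entry at year 4: 1 - exp(-0.225) = 20.1%
- entry at year 6: 1 - exp(-0.025) = 2.5%

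The discontinuation rate is identical throughout; only the time available differs.

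**Step 2: the false gap, worked for A = 5 and h = 0.10.**

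- Share who complete: [exp(-h(T - A)) - exp(-hT)] / (hA) = (0.8825 - 0.5353) / 0.5 = 0.694. Share discontinued: 0.306.
- Mean entry time among completers, as a fraction of accrual, with k = hA = 0.5: 1/(1 - exp(-k)) - 1/k = 2.5415 - 2 = 0.5415.
- Share with the characteristic among completers: 0.80 - 0.40 × 0.5415 = 58.3%.
- Share among the discontinued: (0.60 - 0.6945 × 0.5834) / 0.3055 = 63.8%.
- Gap, discontinued minus completers: 5.4 points, with no true association.

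**Step 3: the same calculation over the range.**

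| Accrual (years) | False gap at h = 0.05 to 0.15 (points) |
|---|---|
| 1.25 | 0.9 to 1.1 |
| 2 | 1.4 to 1.8 |
| 4 | 3.5 to 4.3 |
| 5 | 4.9 to 5.9 |
| any, no drift | 0 |

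**Step 4: masking.** Suppose the characteristic truly lowers the discontinuation hazard by 30% (hazard ratio 0.70). With 5-year accrual and no drift, the gap is -9.3 to -10.4 points. With the 80% to 40% drift it shrinks to about -4.2 to -4.5. With 2-year accrual the loss is small: from -9.7 to -11.6 down to -8.2 to -9.9.

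**Step 5: the alternative measure.** Under a constant hazard, expected discontinuations in any group equal hazard × person-years, so discontinuations divided by person-years return the hazard whatever the entry dates. The rate ratio comes out at 1.00 when there is no association and 0.70 when there is one, in every scenario above.

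**The case against.** Five points can be made on the other side.

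**The size is assumed.** This stands. The protocol states no drift, and without drift the false gap is zero. Sections 9.5 and 9.9.4 refer to a minimum of five years of follow-up for all participants. In a 6.25-year registry that implies 6.25 - 5 = 1.25 years of accrual, and so a gap of about 1 point. However, section 9.5 itself says that this minimum may not be kept, so longer accrual cannot be ruled out.

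**It is within sampling noise.** This largely stands. With 300 participants and 5-year accrual there would be about 51 to 125 discontinued, and the standard error of the gap is roughly 6 to 7 points. The false gap is thus about one standard error. The artefact is nevertheless systematic, and it can offset a real difference.

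**It is a descriptive side table.** This stands too. No formal testing is planned and no decision depends on it. A reader might infer that the incidence rates are distorted as well. They are not affected by this choice, because section 9.7.1 computes them from person-time to event or censoring.

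**It is detail for the SAP.** This stands in part. The SAP may define a completer and may stratify by entry year. But the protocol does not leave the comparison open: two sections name the two groups, and one gives the purpose.

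**Nothing is said about interims.** A reader might infer that the check fails at all six interim reports because nobody has completed by then. "Annual interim report #6" is planned for Q4 2031, before the close in Q2 2032. But no section places this comparison at an interim, and completion is undefined. Only the conditional statement holds: if the comparison were run at an interim, and completion means reaching registry close, there would be no completers.

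**Conclusion.** The point holds in a limited form. The comparison fixed in sections 9.7 and 9.9.4 makes group membership depend on entry date, so it can show a false difference or hide a real one if case mix shifts over accrual. The mechanism follows from the protocol's own entry and follow-up rules. The size does not: under an assumed 80% to 40% drift and exit of 5-15% per year it runs from about 1 point (1.25-year accrual) to 5-6 points (5-year accrual), and it is zero without drift. A steeper assumed drift of 90% to 20% would give 8.6 to 10.4 points at 5-year accrual, but nothing in the protocol supports a shift that large, and it should not be read as the expected error.

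This is a modest weakness in the only attrition check described. It is worth correcting because a better measure is available at almost no cost.

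**What to change.** In sections 9.7 and 9.9.4, replace the discontinued-versus-completer comparison by:

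- registry-discontinuation rates per person-year, with time-to-discontinuation curves, by baseline characteristic, censoring at data extraction those still in follow-up. The curves also guard against a discontinuation rate that changes with time since enrolment, which a single rate would average over;
- the same by reason: consent withdrawal or lost contact, site termination, entry into an interventional trial, and death;
- stopping crovalimab as a separate event, because section 9.2.3 continues follow-up after it.

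These measures need no completer group, so they could also be shown at an interim if wanted.

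The cost is a change of wording in two sections and one extra descriptive table. The data are already planned: section 9.1 records the date and reason for withdrawal, and Table 1 collects crovalimab exposure dates. No primary estimate changes.

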9.7.1 Safety Analyses

No formal statistical testing will be performed. Descriptive statistics will be reported using summary tables and figures (where appropriate). Continuous variables will be summarized using mean, standard deviation, median, range (min–max) and interquartile range. Categorical variables will be summarized using counts and proportions (%).

Additionally, incidence and incidence rate (IRs; in person-years) and their 95% CIs of AESIs, SAEs and AEs will be calculated. The exact 95% CIs will be computed using the Clopper-Pearson method (Clopper and Pearson 1934). For the calculation of IRs, the denominator will be the pooled person-time of all the participants within the cohort. The patient time–at-risk will be calculated from index date until the date of an incident event or censoring, whichever occurs first. All first events occurring during follow-up period will be counted in the total number of events (thus, for each participant, only the first event will be counted) and divided by the total patient-years at risk. In addition, to IRs, incidence proportions will be calculated as proportion of participants with PNH afflicted with each of the AESIs, SAEs, and AEs up to the data extraction date.

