The treatment options available to patients with PNH differ significantly by country and geographical region. The current standard of care (SOC) for PNH involves complement inhibition, which has significantly improved patient outcomes. Allogeneic hematopoietic stem cell transplantation (HSCT) is a curative option that is available in certain countries but presents significant risks. In countries where complement inhibitors are not currently available, management of patients is mainly through supportive care (Cançado et al. 2021).

Crovalimab, a novel, long-acting monoclonal antibody (mAb) targeting C5, has demonstrated efficacy in reducing hemolysis, improving QoL, and potentially offers a more convenient dosing schedule compared to existing therapies (eculizumab and ravulizumab). Overall, crovalimab has shown a well-tolerated safety profile, similar to that of eculizumab in patients with PNH, both in treatment naïve patients and in patients already on treatment with eculizumab or ravulizumab (Roth et al. 2025; Roth et al. 2024).

However, as crovalimab is a new treatment, comprehensive post-marketing surveillance is essential to fully understand its long-term safety profile and potential risks. This is particularly important given the chronic nature of PNH and the need for long-term treatment.

The most commonly reported adverse events (AEs) with crovalimab treatment are pyrexia, headache, infections, infusion and injection-related reactions (IRRs), injection-related reactions (only affecting crovalimab SC administration) and transient immune complex reaction (TICR), also known as Type III hypersensitivity reaction (affecting only patients switching treatments). Meningococcal infection is an important AE of crovalimab treatment, related to its mode of action.

The European Medicines Agency (EMA) and the U.S. Food and Drug Administration (FDA) have requested additional data on specific safety concerns, including:

- Serious infections: Complement inhibition can increase the risk of infections.

- Meningococcal infections: Infections caused by encapsulated bacteria are of special interest, as patients treated with the current SOC have very high-risk to encapsulate infections.
- Hemolysis after discontinuation: The potential for rebound hemolysis upon treatment cessation is high. Nevertheless, the likelihood that a patient with PNH will discontinue treatment with a complement inhibitor without switching to another similar treatment is low.

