9.2 SETTING

This study will analyze individual patient-level data gathered from multiple countries within the Crovalimab Silo. To date, the Crovalimab Silo plans to enroll participants from

Belgium, Canada, France, Germany, Italy, Netherlands, South Korea, Spain, United Kingdom, and the United States. China is under feasibility.

Index Date

The index date is defined as follows:

- To evaluate AESIs and other SAEs and AEs for all participants with PNH, the index date will be defined as the date of enrollment in the Crovalimab Silo.
- To characterize SAEs and AEs for women who are pregnant and pregnancy outcomes, the index date for these outcomes will be defined based on the pregnancy status at the time of silo enrollment. If the participant with PNH is pregnant, the index date will be the date of the silo registry enrollment. If the participant with PNH becomes pregnant after enrollment, the index date will be defined as the date of conception (DOC).
- To assess adverse fetal/neonatal/infant outcomes, SAEs, and AEs at birth and through at least the first year of the infant's life, the index date will be defined as the date of infant birth.
- For breastfeeding-related safety events, the index date will be defined as the date of initiation of breastfeeding for women who are in the Crovalimab Silo before breastfeeding starts or as the date of enrollment for women who join the Crovalimab Silo while breastfeeding.

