9.3.1.2.7 Infusion- and Injection-related Reactions

All IRRs, occurring during or within 24 hours after crovalimab administration will be described. All reactions should also be evaluated to determine if they were related to studied medicinal product infusion or injection, and therefore, captured as a diagnosis (e.g., "infusion-related reaction", "injection-site reaction", or "anaphylactic reaction"). If possible, ambiguous terms such as "systemic reaction" should be avoided. Associated signs and symptoms should also be recorded. If a patient experiences both a local and systemic reaction to the same dose of studied medicinal product, each reaction will be recorded separately, with signs and symptoms also recorded separately on the dedicated Crovalimab Silo eCRF.

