Obstetric history ^g	X		
Pregnancy status, outcome and maternal complications	X	X	X
AEs, adverse fetal/neonatal/infant outcomes and baby complications, including growth and development deficiency ^h		X	X
Breastfeeding information	X	X	X
Vaccination	X	X	X
Fatigue questionnaire ⁱ	X	X	

Data	Baseline (Enrollment Visit) ^a	Follow-up ^b	Participant Discontinuation of Crovalimab/Registr y Completion ^c
------	---	------------------------	--

AE = adverse event; ASEI = adverse event of special interest; FACIT = Functional Assessment of Chronic Illness Therapy; LDH = lactate dehydrogenase; MAVE = major adverse vascular event; PNH = paroxysmal nocturnal hemoglobinuria; SAE = serious adverse event; ULN = upper limit of normal.

- ^a Data from baseline will include information collected in the core and at the enrollment visit.
- ^b Data are expected to be entered in the electronic data capture system approximately every 6 months post-enrollment. Every participant will be followed up during their entire crovalimab treatment and up to 12 months after discontinuation of crovalimab, if they do not start a new complement inhibitor (or 12 weeks if they start a new complement inhibitor).
- ^c After discontinuation from crovalimab, participants with PNH would be followed up for 12 months from the discontinuation date of crovalimab (if they do not start a new complement inhibitor) or up to 12 weeks after discontinuation (if they start a new complement inhibitor).
- ^d Including serious infections, Meningococcal infection, development or worsening of any neurological condition (e.g., axonal neuropathy, multifocal mononeuropathy, etc.), malignancies and hematologic abnormalities, serious hemolysis in participants with PNH who discontinue crovalimab, transient immune complex reactions, and infusion and injection related reactions. Treatment, hospitalizations, outcomes and causality for AESIs, AEs, and SAEs will be also collected.
- ^e Including, but not limited to MAVEs (including thrombosis), packed red blood cell transfusions, breakthrough hemolysis, high disease activity status (evidence of $LDH \geq 1.5 \times ULN$ with any of the following symptoms: fatigue, hemoglobinuria, abdominal pain, shortness of breath, anemia (hemoglobin < 100 g/L), dysphagia, erectile dysfunction, development or worsening of autoimmune disease, bone marrow pathology and hematological disorders, impaired renal function, impaired hepatic function, and death.

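### One whole-cohort person-time denominator for every AESI gives no rate for hemolysis after discontinuation and a TICR rate that is diluted and falls as follow-up accrues

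*Protocol*

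**What the plan says.** Section 9.7.1 gives one rule for the incidence rates of AESIs, SAEs and AEs: "the denominator will be the pooled person-time of all the participants within the cohort". Time at risk is "calculated from index date until the date of an incident event or censoring, whichever occurs first", and "for each participant, only the first event will be counted". For AESIs, Section 9.2 states that "the index date will be defined as the date of enrollment in the Crovalimab Silo". No AESI has its own risk set or time window. Section 9.7.1 adds an incidence proportion for each AESI. Section 9.7.2 adds a comparison of naïve and prevalent new users, subject to sample size.

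Elsewhere the protocol describes narrower risk periods:

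- **TICR.** Section 7 describes it as "affecting only patients switching treatments" and places it at a switch between crovalimab and eculizumab or ravulizumab, in either direction.
- **Hemolysis.** The list of regulatory requests in Section 7 includes "Hemolysis after discontinuation: The potential for rebound hemolysis upon treatment cessation is high". Footnote d of Table 1 (Section 9.3.3) lists the AESI as "serious hemolysis in participants with PNH who discontinue crovalimab". Section 9.3.1.2.5 defines serious hemolysis by LDH and clinical criteria, without tying it to stopping.
- **Infusion and injection reactions.** Section 9.3.1.2.7 covers those "occurring during or within 24 hours after crovalimab administration".

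Section 9.2.3 continues follow-up after discontinuation for up to 12 months, or for 12 weeks if a new complement inhibitor is started.

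**The concern.** An incidence rate is informative when the person-time below the line is time in which the event could have occurred. For infections, malignancy and neurological events, pooled time from enrollment is reasonable. For TICR and for hemolysis after stopping, most of the pooled time carries no risk by the protocol's own description.

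Two consequences follow. The TICR rate mixes the risk at a switch with the length of stable follow-up, so it falls as the registry matures even if the risk at each switch is unchanged. Section 6 plans six annual interim reports, and a reader comparing them could take this for an improving safety profile. For hemolysis, the quantity the regulators asked for is not produced: post-stop events and post-stop time are merged with everything else, and none of the subgroups named in Section 9.7.2 isolates participants who stop.

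**Working it through.** **The plan's own figures.** The protocol states no incidence rate and no total of person-years. Its only AESI calculation is Table 2, which reproduces: at 0.5% prevalence, 1 − 0.995^300 = 77.8%. That table works per participant over the whole follow-up, so it does not bear on the denominator of a rate.

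**TICR.** Inputs: 300 participants and 17.8% with a TICR in the crovalimab trials (both Section 9.5). Assumptions: 50% of the cohort are switchers, 17.8% is the risk among switchers, and events occur early, so that a participant with an event adds almost no person-time.

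- Events = 300 × 0.50 × 0.178 = 26.7.
- Pooled person-years = (300 − 26.7) × T = 273.3 × T, where T is mean follow-up in years.
- T = 1: 26.7 / 273.3 = 9.8 per 100 person-years.
- T = 3: 26.7 / 819.9 = 3.3 per 100 person-years.

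Range:
- 30% switchers: 16.0 / 284.0 = 5.6, falling to 1.9.
- 70% switchers: 37.4 / 262.6 = 14.2, falling to 4.7.
- Section 9.5 does not say whether 17.8% refers to switchers only. If it applies to all 300: 53.4 / 246.6 = 21.7, falling to 7.2.

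The level changes but the threefold fall does not, because with early events the rate is proportional to 1/T.

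**Serious hemolysis, passages side by side.** If the Table 1 footnote governs, only participants who stop can have the event, and whole-cohort time from enrollment is the wrong risk set. If Section 9.3.1.2.5 governs, on-treatment time is at risk and the pooled rate is a valid any-time rate. It is still not a post-discontinuation rate. In that case a first on-treatment episode also ends the participant's time at risk, so a later episode after stopping is not in the rate. Neither reading yields what the regulators requested.

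**Size of the post-stop risk set.** Assumptions: constant stopping rate r of 5% to 15% per year over a 3-year horizon; a share s of 95% to 80% of stoppers start a new complement inhibitor and are followed for 12 weeks (84 days), the rest for 12 months; each stopper is credited with the full window; time lost after an event is ignored.

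- Stoppers = 300 × (1 − e^(−3r)).
- On-drug person-years = stoppers / r.
- Post-stop person-years = stoppers × [s × 84/365.25 + (1 − s) × 1].
- r = 0.05, s = 0.95: 41.8 stoppers; 835.8 on drug; 41.79 × 0.2685 = 11.2 post-stop; pooled 847.0; ratio 75.
- r = 0.15, s = 0.80: 108.7 stoppers; 724.7 on drug; 108.7 × 0.3840 = 41.7 post-stop; pooled 766.5; ratio 18.

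**Infusion and injection reactions.** Here the dilution is pooled time over on-treatment time. The largest value on the grid examined (mean follow-up 2 to 6.25 years, 10% to 40% stopping, 12 weeks or 12 months off drug) is at 2 years, 40% and 12 months: 600 / (600 − 120) = 1.25. The smallest is 1.00.

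**The case against.** The case against has five parts.

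- **The study is descriptive and the pooled rate does not stand alone.** Incidence proportions are also reported, and person-time does not dilute them. This is true, but the proportions still divide by all participants, so they isolate neither switchers nor stoppers.
- **The new-user subgroup separates out many non-switchers.** It would remove a factor of 1/0.7 = 1.4 to 1/0.3 = 3.3 at 70% to 30% switchers. However, it depends on sample size, counts any earlier C5 inhibitor rather than a recent switch, sets no window around the switch, and misses switches away from crovalimab.
- **The statistical analysis plan can add tables.** It can, and Section 9.7.2 leaves further analyses to it. But Section 9.7.1 has already stated the denominator, and the hemolysis inconsistency is in the protocol itself.
- **Footnote d belongs to a data-collection schedule, and the objectives list serious hemolysis without restriction.** This stands. A reader might infer that whole-cohort time is a denominator error for hemolysis under any definition. The documents do not support that: under Section 9.3.1.2.5 it is valid for an any-time rate. What remains is a conflict of definition and a missing post-discontinuation estimate.
- **Reactions recur with dosing.** A reader might infer from the 24-hour window that reaction rates are also diluted many-fold and would decline falsely. That does not hold. Each dose renews the risk, only off-drug time dilutes, and nothing in the protocol says that reactions cluster early.

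Nor should a reader infer that post-stop hemolysis goes unrecorded. Dates and de-/rechallenge are collected and follow-up continues after stopping; the gap is in the analysis.

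**Conclusion.** The point holds for two AESIs. As written, the TICR rate is diluted by time and participants not at risk, and it falls by about the factor by which mean follow-up grows. No rate of serious hemolysis after discontinuation is produced, and Section 9.3.1.2.5 and footnote d of Table 1 disagree on what the event is.

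The sizes are illustrative: about 9.8 against 3.3 per 100 person-years for TICR, and roughly 18- to 75-fold between pooled and post-stop time. They depend on the share of switchers, stopping rates and follow-up, none of which the protocol gives. The TICR decline also assumes that most events follow a switch onto crovalimab; reactions at a later switch away would soften it. The direction of both effects follows from the protocol's own text. For infusion and injection reactions the effect is 1.00- to 1.25-fold and is not a reason to change the plan.

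**What to change.** Keep the pooled incidence rate. Then:

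1. Reconcile Section 9.3.1.2.5, footnote d of Table 1 and the regulatory request in Section 7, so that it is clear which episodes of serious hemolysis count as the AESI.
2. Add to Section 9.7.1, with a matching index date in Section 9.2, a rate and proportion of serious hemolysis among participants who stop crovalimab. Index it at the stop date, run it through the follow-up already specified in Section 9.2.3, and count it regardless of earlier episodes. Report on-treatment serious hemolysis separately.
3. Add TICR risk per switch, among participants switching to or from another C5 inhibitor, within a pre-specified window.
4. Optionally, report infusion and injection reactions over on-treatment person-time or per administration. This is minor.

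The cost is wording in three sections and a few extra tables. Table 1 already collects crovalimab dates and doses and the date of the last previous PNH treatment, and Section 9.2.3 already depends on knowing when a participant stops and whether a new complement inhibitor is started. The post-discontinuation denominator will be small and its interval wide, which is an honest statement of what the registry can say. The change is best made before the first interim report (Q4 2026), so that all reports use the same definitions.
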